5.1.3 Rationale for Dose Selection

In a previous clinical investigation with CGS-200 5% and 10% capsaicin (Study VZU00021), both strengths gave essentially the same degree of pain relief and over essentially the same time course to maximum effect and lasting at least 29 days after cessation of treatment. Both strengths were well tolerated. Based on this, the choice of CGS-200-05 as the high dose Arm in this study is seen as rational. For the low dose Arm, CGS-200-1 was selected on the basis of being a reduction of 5-fold from the 5% dose, which degree of reduction is likely to give a lower response than the 5% dose based on modeling of analgesic responses from 7 days of QD and BID doses

of 0.25% capsaicin in CGS-200 observed in a clinical study of Sponsor's marketed OTC Monograph capsaicin topical product.

5.1.4 Dosage and Administration

The study medication is for external use only and will be administered at the clinic by the subject under the supervision of trained site personnel. Wearing gloves, supplied by the clinic staff, a single dose of the assigned treatment will be topically applied to each knee on each of four dosing days. Both knees will be treated for all subjects, if possible, however only one knee will be the study knee on which assessments are performed. The first application of medication will be at Visit 2 on Day 1 (initiated at Time 0). Dosing on each of the three subsequent treatment days should be performed at the same time of day ± 2 hours in relation to the start time of the initial dose on Day 1.

With the knee relaxed, in a straight and horizontal position, treatment will begin by identifying a 10 cm by 10 cm area where the upper boundary is 1 cm above the patella, the center is aligned with the midline of the patella, and the line bisecting the 10 cm by 10 cm square has 5 cm on either side medially and laterally to the midline of the patella. Each application of the study medication will consist of a single pass of the roller ball over the knee so as to completely cover the designated treatment area. The treatment will be applied continuously beginning at the upper left corner of the square and moving the rollerball horizontally to the upper right corner and moving back and forth in a continuous pattern in a downward progression until the entire square is covered. This should result in moistening the skin providing a thin film of medication (approximately 0.13 mL [or 0.13 gram] of drug product applied to 100 cm² of knee surface, which represents 1.3 mg of solution per cm²). Areas that were already moistened should not be recoated. The study medication should not be applied to a knee if the subject is still experiencing stinging, burning, pruritus, erythema, or scaling from a prior application to that knee. In the case of a dose that is skipped, the subject should return as scheduled for their next visit at which time they may receive the next scheduled application of study medication if their symptoms have subsided. The treatment period will not be extended beyond 4 days.

During the application process, care must be taken not to contaminate the outside of the bottle, other body surfaces, or equipment or other surfaces in the room. Any suspected contamination should be dealt with by washing off the formulation as soon as possible. The subject's knees will remain uncovered for 60 minutes (up to 65 minutes) after dosing to allow for assessments and proper absorption of the study medication. The subject must avoid touching the knee area during this time. The knees will then be cleansed by trained personnel according to specific procedures designed to remove any remaining residual formulation from the surface of the skin. After the area is cleansed, the subject may cover their knees, but should avoid doing so if possible. It is recommended that the subject wear shorts or a skirt during the treatment period rather than long pants. During the four days of treatment, subjects should also avoid exposing the knees to any form of heat (hot water, vigorous exercise, direct sunlight, etc.). If a subject experiences intolerable pain or severe irritation from the study medication, they may apply cold water, ice, or a cold pack or cold compress to their knee. If the subject continues to have unbearable pain, they should contact the study site for help with pain management. In the event of an allergic reaction or medical emergency, the Medical Monitor must be contacted immediately.

Treatment assignment for all subjects enrolled in this study will be double-blind; the subjects and all site personnel and CRO personnel (except for the medical monitor providing safety oversight) involved in this study will not know the treatment given to any subject. Every effort should be made to maintain the study blind.

Subjects will be monitored closely during and after application of treatment for any signs of acute adverse reactions. If an allergic reaction occurs, suggested guidelines are as follows:

- Grade 3 or higher adverse reaction:
 - If treatment is ongoing, it must be immediately and permanently discontinued, the study drug should be washed off, and the subject should be treated symptomatically as clinically indicated.
 - The subject will be followed for safety as clinically indicated until the toxicity resolves, and in the opinion of the investigator, no further follow-up regarding the toxicity is needed. Complete documentation of the event is required.

• Grade 2 adverse reaction:

- If treatment is ongoing, it must be immediately interrupted and the subject should be treated symptomatically as clinically indicated.
- Once the subject has recovered to baseline and, if in the opinion of the investigator the benefit/risk is favorable, consideration can be given to restarting the treatment the next day after pre-medicating with an H2-receptor antagonist and acetaminophen.

• Grade 1 adverse reaction:

 If treatment is ongoing, it may continue, but the subject should continue to be monitored carefully to ensure that ongoing signs and symptoms do not progress and worsen warranting intervention as described above.

5.1.5 Reporting Product Defects

Any defects with the investigational products must be reported *immediately* by the site to the Medical Monitor and Vizuri Health Sciences with further notification to the site monitor.

5.2 CONCURRENT MEDICATIONS

5.2.1 Allowed Regimens

Subjects may continue their baseline medication(s) as long as the medications are not prohibited as outlined in Section 5.2.2. If for any reason deemed necessary by the investigator, a subject requires additional medication(s) or change of dose, the medication(s), dosage change, route of administration, start and stop dates, and the indication for which it was given must be recorded in the source documents and electronic case report form (eCRF).

5.2.2 Prohibited Medications

Subjects should not receive any of the following medications through Day 94 and for the additional times specified below:

- Topical, oral or injectable steroids for 1 month prior to screening, or intra-articular-visco-supplementation within 3 months prior to screening;
- Any capsaicin-containing product on or in the vicinity of the knee within 4 weeks prior to screening;
- Topically applied products (including emollients or moisturizers) on or in the vicinity of the knees within 2 days prior to the first application of study drug;
- Topical or any other therapy on the knees that, in the Investigator's opinion, might affect the study evaluation of signs/symptoms;
- Daytime use of medications or substances (alcohol, benzodiazepines, barbiturates, muscle relaxants, tranquilizers, hypnotics) that could diminish cognitive ability to comply with study procedures;
- Investigational drug, device or therapy within 30 days prior to screening.

5.3 PROHIBITED PROCEDURES

Subjects should not undergo any of the following procedures through Day 94 and for the additional times specified below:

- Anticipates any surgical procedure within 3 months of screening;
- Had surgery on the affected joint within 6 months prior to screening;
- Prosthesis at the index joint.
- Subjects should not shave their knees within 2 days before Day 1 and through Day 5.

6.0 STUDY PROCEDURES

6.1 SCREENING VISIT

Written informed consent must be obtained before any screening procedures are performed that are not considered part of normal patient care. Screening for many subjects will be completed in 2 visits. During the first visit, all screening activities with the exception of obtaining laboratory work should be completed. Prior to this second visit in which laboratory work will be collected, subjects must begin fasting (except water) for chemistry assessment beginning at midnight prior to the blood draw visit. If a subject presents for the first screening visit and has fasted on his/her own since midnight the blood draw may be taken at the first screening visit and a second screening visit will not be required. Table 6–1 shows all the procedures to be conducted at the Screening Visit. Subjects should plan to be in the clinic a minimum 1.5 hours (up to 2 to 3 hours) each visit.

Table 6–1 Screening Procedures

Assessment	Within 28 days of Study Day 1		
Clinic Visit	X		
Informed Consent	X		
Inclusion / Exclusion	X		
Demographics	X		
Medical & Medication History	X		
Physical Exam	X		
Heights & Weight	X		
Vital Signs ^a	X		
Knee X-rays ^b	X		
12-lead electrocardiogram (ECG) ^c	X		
Clinical Laboratory Tests ^d	X		
Serum Pregnancy or Follicle-stimulating hormone (FSH) Test ^e	X		
Application Site Pain, Erythema, Edema, Scaling, Pruritus Assessment ^f	X		
Exploratory Assessment of OA Knee Paing	X		
WOMAC	X		
Assessment of Concomitant Medicationsh	X		

a Vital signs include temperature, blood pressure, heart rate and respiratory rate.

Hematology: complete blood count (CBC) including red blood cells (RBC), hemoglobin, hematocrit, MCV, MCH, MCHC, white blood cells (WBC), differential white cell count, platelet count.

ESR

Chemistry: Blood Urea Nitrogen (BUN), creatinine, uric acid, bilirubin (total), sodium, potassium, calcium, magnesium, phosphorous (inorganic), chloride, bicarbonate, alkaline phosphatase (ALK), aspartate aminotransferase (AST), alanine aminotransferase (ALT), lactate dehydrogenase (LDH), gamma-glutamyl transpeptidase (GGT), creatine phosphokinase (CPK), albumin, total protein, and glucose

Immunoglobulin M (IgM) RF

Urinalysis: pH, protein, glucose, ketones, bilirubin, blood, urobilinogen, specific gravity, leucocytes. Clinically significant abnormal dipstick results will require microscopic analysis.

Knee-X-rays of both knees must be obtained unless films/images performed within 6 months before screening. Copies of film and results will be requested.

^c Standalone 12-lead ECG.

d Clinical Laboratory Tests (Appendix A):

- ^e Serum pregnancy test for premenopausal women; FSH test to confirm postmenopausal status (females only) for up to 2 years after cessation of menses
- Application site pain will be assessed on the NRS (0-10); application site erythema/edema will be assessed using modified categorical Draize test (0-3). [9] Scaling and pruritus will also be scored on a similar categorical scale (0-3). Scoring for application site pain (not related to knee pain) and for erythema, edema, scaling and pruritus. (Appendix F and G).
- Exploratory assessment of OA knee pain (average daily pain and daily worst pain) (Appendix F).
- b Document all medications taken within 90 days of the Screening visit.

6.2 ON-TREATMENT EVALUATIONS:

Table 6–2 shows all procedures to be conducted during Study Days 1 to 4 when study drug is applied in the Clinic.

Table 6–2 On Treatment Evaluations

Assessment		Treatment Days			
TIMEFRAME	1	2	3	4	
Clinic Visit	X	X	X	X	
Randomization	X				
Vital Signs ^a	X	X	X	X	
Urine Pregnancy Test ^b	X				
Application Site Pain, Erythema, Edema, Scaling, Pruritus Assessment ^c	X	X	X	X	
VAS OA Knee Pain Assessment ^d	X	X	X	X	
WOMAC ^e	X				
Exploratory Assessment of OA Knee Painf	X				
Drug Administration	X	X	X	X	
Assessment of Concomitant Medications	X	X	X	X	
AE Assessments	X	X	X	X	

Wital signs include temperature, blood pressure, heart rate and respiratory rate pre-dose on Days 1-4 and at 90 minutes (± 5 min) after applying study drug to knees.

- b Urine pregnancy test at baseline on Day 1 for premenopausal women.
- c Application site pain will be assessed on NRS (0-10); application site erythema/edema will be assessed using modified categorical Draize test (0-3). Scaling and pruritus will also be scored on a similar categorical scale (0-3). Scoring for application site pain (not related to knee pain) will be performed on drug administration Days 1-4 (pre-application [≤30 min], and at 15 (± 5 min), 30 (± 5 min), 60 (± 5 min) and 90 minutes (± 5 min) after application) and on Days 5, 20, and 35. Application site skin reactions (erythema, edema, scaling, pruritus) will be assessed on drug administration Days 1-4 (pre-application [≤ 30 min], and at 15 (± 5 min), 30 (± 5 min), 60 (± 5 min) and 90 minutes (± 5 min) after application). (Appendix E and Appendix F).
- d OA knee pain to be scored on 100mm VAS scale pre-treatment (≤ 30 min) on Days 1-4.
- e WOMAC Pain, Stiffness, and Physical Function will be performed on Day 1 prior to drug administration (≤ 30 min).
- f Exploratory assessment of OA knee pain (average daily pain and daily worst pain) (pre-application [≤30 min]) (Appendix F).

"BASELINE" is defined in this study as the WOMAC scores (pain, stiffness, function) and the VAS OA knee pain score recorded within 30 minutes of the first application of study drug.

6.3 FOLLOW-UP PERIOD EVALUATIONS

Table 6–3 shows all procedures to be conducted during the Follow-up Period (Clinic Days 5, 19, 35, 64 and 94).

Table 6–3 Follow-up Period Evaluations

Assessment	Follow-up Period Days					
TIMEFRAME	5 (24hrs post Day 4 [±4 hrs])	19±3 (Post- Treat Wk 3)	35±3 (Post- Treat Wk 5)	64 (+ 3), (Post-Treat Wk 9)	94 (+ 3) (Post-Treat Wk 13)	Unscheduled, Early Termination, SAE ^e
Clinic Visit	X	X	X	X	X	X
Vital Signs ^a	X				X	X
Physical Exam						X
Clinical Laboratory Tests	X		X		X	X
Application Site Pain, Erythema, Edema, Scaling, Pruritus Assessment ^b	X	X	X	X	X	X
VAS OA Knee Pain ^c	X	X	X	X	X	X
WOMAC ^d	X	X	X	X	X	X
Assessment of Concomitant Medications	X	X	X	X	X	X
AE Assessments	X	X	X	X	X	X
Study Exit		·			X	

Vital signs include temperature, blood pressure, heart rate and respiratory rate.

6.4 BIRTH CONTROL REQUIREMENTS

Female subjects of childbearing potential must agree to use a highly effective method of birth control (defined as those, alone or in combination, which result in a low failure rate, i.e., less than 1 percent per year, when used consistently and correctly) for at least 30 days after last dose of study drug.

Male subjects must agree to use a highly effective method of birth control (defined as those, alone or in combination, which result in a low failure rate, i.e., less than 1 percent per year, when used consistently and correctly) for at least 30 days after last dose of study drug.

Application site pain will be assessed on NRS (0-10); application site erythema/edema will be assessed using modified categorical Draize test (0-3). Scaling and pruritus will also be scored on a similar categorical scale (0-3). Scoring for application site pain (not related to knee pain) will be performed on Days 5 (24 hrs [+/- 4 hrs]), 19 (+/- 3 days), 35 (+/- 3 days), 64 (+/- 3 days) and 94 (+/- 3 days). Application site skin reactions (erythema, edema, scaling, pruritus) will be assessed on Days 5 (24 hrs [+/- 4 hrs]), 19 (+/- 3 days), 35 (+/- 3 days), 64 (+/- 3 days) and 94 (+/- 3 days). (Appendix E and Appendix F).

^c VAS OA knee pain will be performed on Days 5 (24 hrs [+/- 4 hrs]), 19 (+/- 3 days), 35 (+/- 3 days), 64 (+/- 3 days) and 94 (+/- 3 days).

WOMAC Pain, Stiffness, and Physical Function will be performed on Days 5 (24 hrs [+/- 4 hrs]), 19 (+/- 3 days), 35 (+/- 3 days), 64 (+/- 3 days) and 94 (+/- 3 days).

e Refer to Section 6.5 for assessments to be completed at time of SAE, early termination or unscheduled visit.

The acceptable methods of birth control are:

- Implanted, injected, or oral contraceptives
- Intrauterine devices
- Barrier methods (male condom, female condom, diaphragm)
- Sexual abstinence (when this is the preferred and usual lifestyle of the subject)
- Male subjects who have had a vasectomy
- Female subjects who have had a hysterectomy, tubal ligation, or bilateral salpingectomy or women of postmenopausal status

In addition, male subjects must not donate sperm during the study and for 30 days after the last dose of study drug.

6.5 ASSESSMENTS AT TIME OF SAE, EARLY TERMINATION OR UNSCHEDULED VISIT

Additional activities may be performed at the Investigator's discretion at the onset of an SAE, when subjects are prematurely taken off study, and/or for an unscheduled visit.

- Assess vital signs (BP, HR, RR, and T)
- Perform abbreviated symptom-driven physical exam (PE)
- Application site pain will be assessed on numerical pain rating scale (0-10);
 application site edema will be assessed using categorical Draize test (0-3).
 Scoring for application site pain (not related to knee pain) and for erythema and edema will be performed at Early Termination and at Unscheduled Visits.
- VAS OA knee pain and WOMAC will be performed at Early Termination and at Unscheduled Visits.
- Collect blood:

For local laboratory analysis:

- CBC with automated differential and platelets, and serum chemistry
- Document AEs and concomitant medications

6.6 STUDY BLOOD DRAW VOLUME

The total blood volume to be collected during the study is approximately 60 ml (two ounces).

6.7 RECOMMENDATIONS FOR MANAGEMENT OF POTENTIAL TOXICITIES

6.7.1 Allergic Reaction, Burning, or Pruritus

In the case of any life-threatening event occurring during the treatment, the study drug must be immediately and permanently discontinued. While corticosteroids are strongly discouraged, they may be used if they are necessary for the safety of the subject.

• Rash/pruritus/urticaria

- If subject develops rash, pruritus, or urticaria, interrupt treatment if it is ongoing and promptly assess subject for any other associated signs/symptoms (e.g., hypotension, fever, respiratory distress).
 - Consider treating with H2 receptor antagonists as clinically indicated.
 If rash / pruritus / urticaria is isolated and resolves either spontaneously or with intervention, treatment with the study drug may be restarted.

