6.9.3 Stopping Criteria

Any \geq Grade 3 event considered related to the study drug and occurring during administration of the study drug will result in its permanent discontinuation for that subject. The Medical Monitor should be notified immediately and the subject should be followed for safety as clinically indicated until the toxicity resolves and in the opinion of the investigator, no further follow-up regarding the toxicity is needed.

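### Protocol Sections 6.7.1 and 5.1.4 contradict each other on rash, pruritus or urticaria at Grade 1 and at non-life-threatening Grade 3, and set different restart conditions at Grade 2

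*Protocol*

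**What the plan says.** Four parts of the protocol govern what happens to treatment after a skin or allergic reaction.

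- **Section 6.7.1 (Allergic Reaction, Burning, or Pruritus)** has no grades. It says: "If subject develops rash, pruritus, or urticaria, interrupt treatment if it is ongoing and promptly assess subject for any other associated signs/symptoms". On resumption it says: "If rash / pruritus / urticaria is isolated and resolves either spontaneously or with intervention, treatment with the study drug may be restarted". Its only permanent stop reads: "In the case of any life-threatening event occurring during the treatment, the study drug must be immediately and permanently discontinued".
- **Section 5.1.4 (Dosage and Administration)** has a graded list, introduced as suggested guidance for an allergic reaction. At Grade 1: "If treatment is ongoing, it may continue, but the subject should continue to be monitored carefully". At Grade 2 the application must be interrupted; once the subject is back to baseline and the investigator judges benefit/risk favorable, "consideration can be given to restarting the treatment the next day after pre-medicating with an H2-receptor antagonist and acetaminophen". Under the entry "Grade 3 or higher adverse reaction", ongoing treatment is stopped at once and permanently.
- **Section 6.9.3 (Stopping Criteria)** says that any Grade 3 or higher "event considered related to the study drug and occurring during administration of the study drug will result in its permanent discontinuation for that subject".
- **Sections 3.2 and 6.9.2** define a dose-limiting toxicity (DLT) and make it a permanent stop. Section 3.2 sets a Grade 3 threshold for listed categories, including immune reactions and reactions at the administration site, and a Grade 2 threshold for any other adverse event apart from pre-existing OA-related conditions.

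Sections 6.7.1 and 5.1.4 do not cite each other, and no precedence clause says which prevails.

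**The concern.** A site facing the same reaction can take opposite actions depending on which section it consults. Two things are at stake.

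The first is safety. A subject with a Grade 3 reaction that is not life-threatening and later resolves could be treated again under 6.7.1, although 5.1.4 and, for related events during administration, 6.9.3 rule that out.

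The second is delivered dose. Applications are meant to stay on for 60 minutes. If some sites interrupt for mild itch and others do not, contact time varies by site. Because itch was commoner on active drug than on vehicle in the earlier controlled study, it could vary by arm as well. The tolerability comparison uses AUCs of scores at 0, 15, 30, 60 and 90 minutes (Protocol 9.5.4, SAP 6.5), so an interrupted application feeds into it directly. The comparison of 5% with 1% also assumes that each arm received its planned exposure.

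**Working it through.** The plan gives no figure on this point, so there is none to reproduce. The check sets the texts side by side, grade by grade.

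| Grade | 6.7.1 | 5.1.4 list | 6.9.3 | Result |
|---|---|---|---|---|
| 1 | Interrupt | May continue, with monitoring | Not triggered | Contradiction on the ongoing application |
| 2 | Interrupt; restart if isolated and resolved | Interrupt; restart may be considered the next day after recovery to baseline, favorable benefit/risk and premedication | Not triggered | Same actions, different restart conditions |
| 3, not life-threatening | Interrupt; restart if isolated and resolved | Permanent stop | Permanent stop if related and during administration | Contradiction on restart |
| Life-threatening | Permanent stop | Permanent stop | Permanent stop if related and during administration | Agreement |

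**Can these cases occur?** Under Appendix B (RCTC v2.0), Grade 1 pruritus is localised and transient. Generalized urticaria that responds to medication is Grade 2. Itch that stays poorly controlled on treatment, and urticaria that persists on medication, are Grade 3; neither is necessarily life-threatening. The general description of Grade 3 in that appendix includes reversible symptoms, so a Grade 3 reaction that later resolves is possible.

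**DLT rule.** A Grade 2 rash or urticaria that falls outside the listed categories of Section 3.2 would be caught by the residual Grade 2 criterion. Section 6.9.2 then requires a permanent stop, while both 6.7.1 and 5.1.4 allow restart. A reaction at the application site, or one classed as an immune reaction, has the Grade 3 threshold instead, so this conflict depends on classification.

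**Scope.** The 5.1.4 list is introduced for an allergic reaction. The title of 6.7.1 names allergic reaction as well as burning and pruritus, and RCTC item A1 grades urticaria as an allergic reaction. The two sections therefore overlap. Neither says which one governs the local itch expected from capsaicin.

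**Scale.** Inputs: pruritus in 56% of CGS-200-5 and 31% of vehicle subjects in VZU00023 (Protocol 1.3), and 40 subjects per arm (Protocol 3.1). Assuming those rates carry over:

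- CGS-200-5: 0.56 × 40 = 22.4 subjects with pruritus
- Vehicle: 0.31 × 40 = 12.4 subjects with pruritus
- Difference: 22.4 − 12.4 = 10.0 subjects

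These are subjects with any pruritus, not interrupted applications. Section 6.7.1 interrupts only an ongoing application, so itch that starts after wash-off interrupts nothing, and Section 1.3 does not say when the itch occurred. The counts are therefore ceilings for interruption due to itch. That study's summary gives no rate for rash or urticaria.

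**The case against.** The strongest reply is that the sections cover different events. Section 1.4.1 lists possible allergic reactions separately from the effects of topical capsaicin, which include pruritus. On that reading, mild itch at 15 minutes is a local effect outside the 5.1.4 list and only 6.7.1 applies. This stands in part: scope is ambiguous for local itch. It does not remove the contradiction, because 6.7.1 covers allergic reactions by its own title and urticaria falls under both.

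A second reply is that 5.1.4 and 6.7 are advisory while 6.9.2 and 6.9.3 are firm, and Section 6.10 removes subjects with a DLT from treatment. Re-exposure after Grade 3 would need a site to overlook those rules. This lowers the likelihood, but no text says that the stopping criteria override 6.7.1, which is where a site would look for pruritus. The 5.1.4 list also uses mandatory wording at Grades 2 and 3.

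Third, SAP 7.1 summarises the percentage applied, the reason for an incomplete dose and the application duration by arm. A difference in exposure would therefore be visible. It would not be prevented.

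A reader might go further in three ways that the documents do not support:

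- *That the sections conflict at every grade.* At Grade 2 both interrupt and both allow restart, and for life-threatening events they agree.
- *That 6.7.1 allows restart without conditions.* It requires prompt assessment and a reaction that is isolated and resolved. Section 5.1.4 separately bars application to a knee that still has pruritus, erythema or scaling.
- *That 47 to 57 of 120 subjects would receive conflicting instructions.* That sum (12.4 + 22.4 + 12.4 = 47.2, to 12.4 + 22.4 + 22.4 = 57.2) assumes a rate for the 1% arm, places every itch within an ongoing application and puts all of it under both sections.

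**Conclusion.** The inconsistency is real, in limited form. Where their scopes overlap, 6.7.1 and 5.1.4 contradict each other at Grade 1 on interrupting and at non-life-threatening Grade 3 on restarting; at Grade 3, 6.7.1 also contradicts 6.9.3 for related events during administration. At Grade 2 the difference lies in the restart conditions, with a possible further conflict through the DLT rule.

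Local reactions in VZU00023 were generally Grade 1 and at highest Grade 2. If that pattern and the pruritus rates carry over from a Dominican Republic population, the Grade 1 conflict may arise often, and more often on active drug. The Grade 3 conflict should be rare but carries the greater safety weight. The number of interrupted applications, the contact time lost and any resulting bias cannot be derived from the documents. The textual contradiction depends on none of these assumptions. No view is taken here on which clinical rule is right.

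**What to change.** Reconcile Protocol Sections 3.2, 5.1.4, 6.7.1, 6.9.2 and 6.9.3 so that each RCTC grade of rash, pruritus or urticaria carries one action for the ongoing application and one for later applications. State whether expected local itch falls under the allergic-reaction list, and how a Grade 2 rash or urticaria is classified for the DLT definition. Keep the text in one section and replace the others with a cross-reference. Reconciling 6.7.1 with 5.1.4 and 6.9.3 alone would leave the Grade 2 DLT question open. The sponsor's medical lead decides which rule stands.

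The cost is a wording amendment and a notice to sites, with no new visit, procedure or staff. The exposure summaries already planned in SAP 7.1 can show whether interruptions differ by arm.
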